2.7. Training and experience needed

The procedure itself should be performed by vascular surgeons and/or interventionalists experienced in interventional techniques such as complex percutaneous transluminal angioplasty and stenting in the lower limb. Study investigators will be selected based on their experience in performing below-the-knee interventions and duly trained by LimFlow SA on the percutaneous deep vein arterialization specific medical procedure. In order to avoid a learning curve bias, each study investigator will be required to first perform at least one (1) successful revascularization in a “roll-in” subject. “Roll-in” subjects will be included the study but excluded from the endpoint analysis. In addition, a LimFlow SA representative will attend the treatments performed in each site in order to assist the physician on technical issues as well as to ensure that treatment characteristics and potential complications are duly recorded.

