4.6. Steps that will be taken to control or mitigate the risks

The following steps have or will be taken by LimFlow SA to control or mitigate the risks during the course of this post-market study:

- The use of standard medical grade materials that have been thoroughly characterized and tested to assure biocompatibility.
- Extensive pre-clinical evaluation including in vitro bench testing, animal and cadaver study.
- The well-established, standard nature of the endovascular procedures and techniques to be used.
- The ability to quickly and safely remove the LimFlow System from the procedure; the physician may elect to discontinue the use of the device at any time in favour of alternate devices.
- Frequent follow-up visits are conducted in the first year post-operatively to allow for systematic monitoring and surveillance of the index limb, allowing for early detection of hemodynamically significant stenoses in the graft that may occur in the absence of obvious symptoms.
- Potential subjects will be screened by an independent committee to ensure that all subjects meet defined eligibility criteria.
- Investigators will receive device training and will be proctored for their first case, and then for as many cases as they deem necessary to perform the procedure proficiently.

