6.1. General

6.1.1. Type of clinical investigation

This study is a single-arm, open-label, prospective, post-market follow-up study to be conducted on up to 25 eligible patients (roll-in subjects plus 20 analysis subjects) with a twelve-month follow-up period. This study was designed and is to be conducted in compliance with the ISO 14155:2020 standard.

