6.3.3. Point of enrolment

Once any component of the LimFlow System is introduced into the body, the subject will be considered to be enrolled in the study and subject to all follow-up requirements. If the device is introduced but implantation is either not attempted or unsuccessful, subjects will be followed through 30 days for safety only, or through resolution or stabilization of any device- or procedure-related adverse events, whichever is longer; those subjects will then be exited from the study and will not be replaced. In addition, "roll-in" subjects performed to avoid a learning curve bias will be included the study but excluded from the endpoint analysis. In some instances, "roll-in" subjects within the study may not be required for any study site who has performed LimFlow System procedures outside the study in the commercial setting.

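### Roll-in is required per investigator (2.7) but can be waived per site (6.3.3), so an operator's first case may enter the endpoint analysis and the learning-curve control is not assured

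*Combined protocol and SAP*

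**What the plan says.** Section 2.7 gives the purpose, "In order to avoid a learning curve bias", and the rule: "each study investigator will be required to first perform at least one (1) successful revascularization in a “roll-in” subject". The unit is the individual operator, the condition is a success, and no exception is stated.

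Section 6.3.3 repeats the purpose and says that roll-in subjects "will be included the study but excluded from the endpoint analysis". It then adds that in some instances, which it does not define, roll-ins "may not be required for any study site who has performed LimFlow System procedures outside the study in the commercial setting". Here the unit is the site. No minimum number of cases, success or link to the study operator is required.

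Section 4.6 has a separate safeguard, also set per investigator: "Investigators will receive device training and will be proctored for their first case". Section 6.1.1 gives the numbers as "up to 25 eligible patients (roll-in subjects plus 20 analysis subjects"), and 1.6.2 and 6.3.5 agree.

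**The concern.** The roll-in exists to keep an operator's first LimFlow case out of the reported results. A site's commercial record says nothing about an investigator at that site who took no part in it, and a commercial case that failed would not meet the standard in 2.7. Under the site-level waiver, whether a first case is analysed can depend on the history of the hospital instead of the experience of the operator.

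Technical and procedural success are the endpoints closest to operator skill. Amputation-free survival can also be touched. Under 6.3.3 a subject whose implantation is unsuccessful is followed for safety only, for 30 days or until related events settle, then exits and is not replaced. A failed first case in the analysis set could therefore also lose its twelve-month outcome. Section 7.1 plans to pool these data with the US feasibility study, which is a further reason for the analysis set to rest on one clear experience rule.

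**Working it through.** **Step 1. Can the two rules be read together?** Under 2.7 the qualifying success must occur in a roll-in subject, and roll-in subjects are study subjects. Read literally, no commercial case can satisfy 2.7. Section 6.3.3 must therefore be an exception to it, and the terms of 6.3.3 decide who is excused. Those terms name only the site. No other section restores an operator-level condition.

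**Step 2. Apply both rules to each kind of operator and site.**

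| Operator | Site | 2.7 | 6.3.3 | Operator's first study case |
|---|---|---|---|---|
| No LimFlow case | No commercial cases | Roll-in | No waiver | Excluded |
| No LimFlow case | Commercial cases by others | Roll-in | Waiver possible | May be analysed, although it is a first LimFlow case |
| Own successful commercial case | Same site | Roll-in | Waiver possible | May be analysed; not a first LimFlow case |
| Any | Only commercial case failed | Roll-in | Waiver possible | May be analysed without any prior success |

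Rows 1 and 2 describe the same inexperience with different outcomes. Row 4 shows that the waiver drops the success condition as well as the operator condition.

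**Step 3. Weight of one case.** With 20 analysis subjects (6.1.1, 6.3.5), each first case is 1/20 = 5% of the set.

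**Step 4. Possible shift (illustration only).** The documents give neither the number of first cases analysed, k, nor the drop in success rate for a first case, d. If the other subjects succeed at rate p, the expected rate is [(20 − k)p + k(p − d)]/20 = p − (k/20)d, so the shift is (k/20) × d.

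| k | d = 10 points | d = 20 points | d = 40 points |
|---|---|---|---|
| 1 | 0.5 | 1.0 | 2.0 |
| 2 | 1.0 | 2.0 | 4.0 |
| 5 | 2.5 | 5.0 | 10.0 |

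Entries are percentage points.

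**Step 5. Scale.** For an assumed 14/20 (70%), the exact (Clopper-Pearson) 95% interval runs from 45.7% to 88.1%, a width of 88.1 − 45.7 = 42.4 points. One or two first cases would move the estimate by far less than that.

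There is no plan figure to reproduce: section 7.2 states that the sample size was not derived statistically.

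**The case against.** The best answer is that 6.3.3 is permissive. It applies in some instances and says only that roll-ins may not be required, so the sponsor could grant the waiver solely where the study operator did the commercial cases. The investigator-level rule in 2.7 also remains in the text, and nothing shows a first-time operator working at a commercially experienced site. This stands as a limit on the conclusion: a reader might infer that first cases do enter the analysis and that the control fails, and the documents do not support that. It does not remove the conflict, because the discretion has no stated criterion.

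Mitigation is real too. Investigators are selected for below-the-knee experience, trained and proctored for the first case, and a company representative attends treatments (2.7, 4.6). These measures may reduce any first-case deficit. None of them takes a first case out of the endpoint analysis, and the plan excludes roll-in cases even though the same measures apply to them.

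The study is also descriptive, with no hypothesis or success threshold, so no formal decision turns on a shift of a few points. That stands, and it bounds the importance of the point.

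A reader might also infer that the waiver threatens the 20 analysis subjects. The effect runs the other way. The cap leaves at most 25 − 20 = 5 roll-in places if the 20 are filled, and a waiver uses fewer of them. Whether five places are enough depends on how many investigators need a roll-in and how often roll-ins succeed. The text available for review gives neither, so no probability of a shortfall is offered.

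**Conclusion.** The point holds as a conflict between two stated rules. Section 2.7 conditions analysed cases on the operator's own success, while 6.3.3 can lift that condition because of procedures at the site, whoever performed them and however they ended. A first-time operator's first case may therefore be analysed at one site and excluded at another, and the learning-curve control is not assured.

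The only firm size is 5% of the 20 analysed subjects per such case. The shifts of 0.5 to 10 points shown above rest wholly on assumed values of k and d, and no bias can be derived from the documents. With one or two such cases, even a large first-case deficit would be small against the sampling uncertainty at n = 20. The reason to act is the ambiguity about whose results the analysis set describes, together with the low cost of repair. A large bias has not been shown.

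**What to change.** Reconcile 6.3.3 with 2.7 on one unit. In 6.3.3, let roll-in status, meaning exclusion from the endpoint analysis, be waived for an investigator who has personally performed at least one successful LimFlow procedure outside the study. State that the site's record alone does not qualify, and add a cross-reference in 2.7 so that the exception is visible there. This concerns analysis status only and leaves training and proctoring as they are.

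For subjects already enrolled under a site-level waiver, flag each case that was the operator's first LimFlow procedure, using the operator's identity and the sponsor's record of commercial cases. Report how many analysed subjects are flagged, and give the endpoints with and without them. The intra-procedure parameters listed in 6.4.3 do not include the operator, so check that this is captured elsewhere and add it if it is not. Section 6.3.5 expects enrolment to end by October 2022, so the flag and the paired report can still be done even if the text change comes too late for most subjects.

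The cost is a sentence in the protocol, one data flag and one extra set of summaries. A few subjects may move from analysis to roll-in, so the analysis set may be slightly smaller. The loss of precision is modest: an assumed 13/18 has an exact 95% interval of 46.5% to 90.3%, a width of 43.8 points against 42.4 for 14/20.

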6.3.4. Criteria and procedures for subject withdrawal or discontinuation

Patients are withdrawn from study if signed informed consent is withdrawn or when lost to follow-up (if a patient is not able to be contacted within three phone calls, the site shall send a letter requesting response from the subject and contact the patient general practitioner in order to check on the patient's condition; if the site or service receives no response, the patient may be considered lost-to follow-up at that time). Early study exit will also occur if the patient reaches the primary study endpoint either in death, or major amputation of the treated limb. Reason for the study discontinuation must be recorded in the source documentation and on the electronic Case Report Form (eCRF).

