6.1.4. Methods and timing for assessing, recording, and analysing variables

Timing for performing visits and assessing variables during the study follow-up period are presented in Table 4 below. Additional post-treatment evaluations performed outside of the follow-up window will be considered “unscheduled”.

Table 4. Time windows

Visit	Target	Interval	Minimum	Maximum
Two (2) weeks	15 days	± 5 days	10 days	20 days
One (1) month	30 days	± 7 days	23 days	37 days
Two (2) months	60 days	± 10 days	50 days	70 days
Three (3) months	90 days	± 14 days	76 days	104 days
Six (6) months	180 days	± 14 days	166 days	194 days
Nine (9) months	270 days	± 14 days	256 days	284 days
Twelve (12) months	360 days	± 28 days	332 days	388 days

All variables will be recorded on electronic Case Report Forms (eCRFs) specifically designed for the study and provided by LimFlow SA to the investigational centres. Collected variables will be analysed using IBM SPSS statistics software, version 17 or later.

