6.4.4. Follow-up visits

Sites shall maintain a contact log recording the attempted follow-up visits, scheduled at one month, three months, six months, nine months, and twelve months. If a patient is not able to be contacted within three phone calls, the site shall send a letter requesting response from the subject and contact the patient general practitioner in order to check on the patient’s condition. If the site or service receives no response, the patient may be considered lost-to-follow-up at that time.

Follow-up and wound care are to be performed on-site under direct supervision of a study investigator. Patient wounds should be treated in accordance with the TIME guidelines or following similar recommendations.¹¹⁻¹⁷ An arteriography should be performed in case of suspected stent graft occlusion, as per standard practice.

Day 015: two weeks

At 15 days post-treatment, subjects will be examined during a clinic visit and the following assessment will be performed:

- Wound pictures and assessment
- Pain assessment
- Perfusion assessment (TcPO₂, ICG i.v. injection, white-light spectroscopy with laser Doppler, etc.—optional)
- Adverse events
- Review of medications (antiplatelets/anticoagulants and antibiotics regimen)

Day 030: one month

At 30 days post-treatment, subjects will be examined during a clinic visit and the following assessment will be performed:

- Rutherford classification
- WIFL (Wound – Ischaemia – foot Infection) classification
- Wound pictures and assessment
- Pain assessment
- Perfusion assessment (TcPO₂, ICG i.v. injection, white-light spectroscopy with laser Doppler, etc.—optional)
- Duplex ultrasound
- Adverse events
- Review of medications (antiplatelets/anticoagulants and antibiotics regimen)

Day 060: two months

At 60 days post-treatment, subjects will be examined during a clinic visit and the following assessment will be performed:

- Rutherford classification
- WIfI (Wound – Ischaemia – foot Infection) classification
- Wound pictures and assessment
- Pain assessment
- Perfusion assessment (TcPO₂, ICG i.v. injection, white-light spectroscopy with laser Doppler, etc.—optional)
- Duplex ultrasound
- Adverse events
- Review of medications (antiplatelets/anticoagulants and antibiotics regimen)

Day 090: three months

At 90 days post-treatment, subjects will be examined during a clinic visit and the following assessment will be performed:

- Rutherford classification
- WIfI (Wound – Ischaemia – foot Infection) classification

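### One unanswered round of contact lets a site class a subject as lost and so withdrawn, and the plan specifies no later check of survival or limb status

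*Combined protocol and SAP*

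**What the plan says.** Section 6.3.4 makes loss to follow-up a ground for withdrawal: "Patients are withdrawn from study if signed informed consent is withdrawn or when lost to follow-up". It sets the steps that come first: "if a patient is not able to be contacted within three phone calls, the site shall send a letter requesting response from the subject", and the site must also "contact the patient general practitioner in order to check on the" patient's condition. Then, "if the site or service receives no response, the patient may be considered lost-to follow-up at that time".

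Section 6.4.4 repeats the rule almost word for word ("If the site or service receives no response, the patient may be considered lost-to-follow-up at that time"). It also asks sites to keep a log of attempted visits, "scheduled at one month, three months, six months, nine months, and twelve months". Tables 4 and 5 schedule seven follow-up visits. The two that the log sentence omits are week 2 and month 2, the latter appearing in Table 4 as "Two (2) months 60 days ± 10 days 50 days 70 days".

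Other provisions bear on the point:
- Section 18 defines the primary endpoint as a percentage of subjects alive with the limb kept.
- Section 6.1.6 does not replace subjects who drop out after the procedure.
- Section 7.5 counts missing data and shows losses in an accountability tree, with no further rule.
- Section 8 lists obtaining data from other sources as a site-training topic.

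**The concern.** The rule requires no minimum number of missed visits and no waiting period. A subject who cannot be reached around month 1 can be classed as lost then, and 6.3.4 turns that into withdrawal. Such a subject might well be reachable at month 3, or might return to the same hospital for an amputation, but nothing in the plan tells the site to look.

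The primary endpoint needs only two facts: whether the subject is alive and whether the index limb has been amputated above the ankle. Hospital or general practitioner records can supply both, so a missed visit need not become an unknown outcome. The cohort is small, drop-outs are not replaced, and section 7.5 has no rule for unknown outcomes, so preventing avoidable loss is the main protection the endpoint has.

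The safety aim is affected too. Section 5.2 gives incomplete knowledge of late complications as a reason for the study, and those are the events that go unrecorded if follow-up stops early.

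**Working it through.** **Step 1. What the text requires, in order.**

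| Stage | Required by the plan? | Where |
|---|---|---|
| Three calls, then letter and general practitioner contact | Yes | 6.3.4, 6.4.4 |
| Repeat of the sequence before loss is declared | No | not found |
| Declaration of loss after no response | Permitted, not obligatory | 6.3.4, 6.4.4 |
| Withdrawal once lost | Yes | 6.3.4 |
| Renewed contact at the next scheduled visit | Not specified | not found |
| Return of a subject who reappears | Not specified, not forbidden | not found |
| Survival and limb-status check at month 12 | Not specified | not found |

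**Step 2. Time at stake.** In Table 4 the month-1 window closes on day 37 and the month-12 window on day 388. The longest period in which status could still be learned for a subject lost at month 1 is 388 − 37 = 351 days. This is a maximum, because a letter and a general practitioner enquiry take time before loss can be declared.

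**Step 3. Effect on the primary endpoint.** The plan gives no loss rate and no expected amputation-free survival, and section 7.2 says that the sample size was not derived statistically, so there is no planned figure to reproduce. Inputs: N = 20 analysis subjects (6.3.5); L lost subjects, assumed 1 to 4; 6 known events, assumed.

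- All lost subjects event-free: (20 − 6)/20 = 14/20 = 70%
- All lost subjects with an event: (14 − L)/20
- Lost subjects left out of the denominator: (14 − L)/(20 − L)
- Width of the range: L/20

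| L | Best | Worst | Lost left out | Width |
|---|---|---|---|---|
| 1 | 70% | 13/20 = 65% | 13/19 = 68.4% | 5 points |
| 2 | 70% | 12/20 = 60% | 12/18 = 66.7% | 10 points |
| 3 | 70% | 11/20 = 55% | 11/17 = 64.7% | 15 points |
| 4 | 70% | 10/20 = 50% | 10/16 = 62.5% | 20 points |

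The width does not depend on the assumed number of events.

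**Step 4. Direction.** Take L = 2 and leave the lost subjects out, which gives 66.7%. If both had events the true figure is 60%, so the estimate is 6.7 points too high. If one did, the true figure is 13/20 = 65% and the estimate is 1.7 points too high. If neither did, the true figure is 70% and the estimate is 3.3 points too low. The error can go either way.

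**Step 5. Chance that it arises.** The chance of at least one loss among 20 is 1 − (1 − p)^20. At assumed loss rates of 5%, 10%, 15% and 20% it is 64%, 88%, 96% and 99%.

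**Step 6. Scale against sampling error.** The exact (Clopper-Pearson) 95% interval for 14/20 is 45.7% to 88.1%. One or two unknown outcomes move the estimate by less than that, but the interval does not reflect selective loss.

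**Step 7. Effect of the change.** If status is recovered for all lost subjects, the width in Step 3 falls from L/20 to 0. N stays at 20.

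**The case against.** The plan does more than its silence after withdrawal suggests. Three calls, a letter and an enquiry to the general practitioner are a reasonable effort, and the last is itself a third-party check on the patient. If the practitioner reports an admission, an amputation or a death, it is hard to say that there was no response. The classification is also permissive. Section 8 includes other data sources in site training, section 6.5 makes monitors responsible for pursuing incomplete data, and section 14.4 follows subjects with adverse events to the end of the study or to resolution. The study is descriptive, with no formal hypothesis.

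These points stand, and they rule out several stronger readings that a reader might infer:
- **One missed contact is enough.** It is not. The whole sequence must go unanswered.
- **Withdrawal is permanent and later outcomes are not sought.** The text neither bars return nor forbids later enquiry. It specifies neither.
- **Week-2 and month-2 visits are not chased.** The five-visit list describes the contact log. The contact sequence in 6.3.4 is tied to no visit, and 6.4.4 sets out both clinic visits in full. The mismatch is a minor reconciliation point.
- **Amputation-free survival is biased upward.** That needs lost subjects to fare worse and to be dropped from the denominator. The first is plausible, given the mortality of up to 20% at 6 months cited in section 3.2, but is not shown. The second is not stated anywhere in the plan.

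The objection does not supply the missing step. A training topic, a monitoring duty and a rule for subjects with adverse events do not amount to a check of survival and limb status for someone already classed as lost.

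**Conclusion.** The concern holds as a gap in the follow-up rule. One exhausted contact sequence is sufficient for a site to class a subject as lost, 6.3.4 then withdraws that subject, and the plan specifies nothing afterwards to recover survival or limb status through month 12. Following the rule as written can therefore discard primary-endpoint outcomes that could have been learned.

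The size is 5 percentage points of best-to-worst range for each subject of unknown status, on a base of 20. That much is arithmetic. How many subjects would be lost, how many events there would be, and which way the estimate would move are assumptions. This does not invalidate the study. It is an inexpensive improvement that should be made, and it matters more here because the cohort is small and drop-outs are not replaced.

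**What to change.** Amend 6.3.4 and 6.4.4 as follows:
1. Record non-response at a visit as a missed visit, not as withdrawal. The subject stays on schedule, and contact is attempted again at each later scheduled visit.
2. Let a subject who reappears resume visits.
3. Before classing a subject as lost for the primary endpoint, make a final check at the 12-month window (days 332 to 388) of hospital and general practitioner records. Record the date last known alive and the limb status, within the consent given.
4. Reconcile the five visits in the contact-log sentence of 6.4.4 with the seven in Tables 4 and 5.

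If less change is preferred, the month-12 check in item 3 alone would address most of the primary-endpoint concern, though not the gap in the adverse-event record.

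The cost is amendment wording and a few extra calls or record checks per missing subject, with no extra clinic visits and no change to treatment. Version 4.4 (July 2022) expected enrolment to run to the end of October 2022 with twelve months of follow-up after that, so at that version there was still follow-up to protect.
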